# APPANDIX 2 Clinical Laboratory Assessments

Table 3: Protocol-Required Laboratory Assessments

Hematology	
White blood cell (WBC) count a	Hemoglobin
Red blood cell (RBC) count b	Hematocrit
Platelet count	HbA1c
Clinical Chemistry	
Alanine aminotransferase (ALT)	Phosphorus
Albumin	Potassium
Alkaline phosphatase (ALP)	Sodium
Aspartate aminotransferase (AST)	Total bilirubin
Bicarbonate	Direct bilirubin
Chloride	Total Protein
Cholesterol (full lipid panel on Day 1 and EoT only)	Triglycerides
Creatinine	Urea
Calcium	Gamma-glutamyl transferase (GGT) c
Glucose	Magnesium
TSH (Screening)	Multiple biochemical analysis (MBA) c
	Amylase
	Lipase
Urinalysis	
Dipstick:	Microscopic:
Nitrite	WBC
Protein	RBC
Glucose	Epithelial cells
рН	Casts (specify)
Specific gravity	
Ketones	
Bilirubin	
Urobilinogen	
Leucocyte Esterase	

DI I	
Rlood	
Diood	

<sup>a Differential white blood cell count will include percentages for neutrophils, lymphocytes, monocytes, eosinophils, and basophils and absolute counts for neutrophils, lymphocytes, monocytes, eosinophils, and basophils.

Table 4: Pre-Defined Limits of Change for Laboratory Parameters and Electrocardiogram

Hematology	
Hemoglobin (g/dL)	1. Decrease ≥ 1.5 g/dL
	2. Increase $> 2.0 \text{ g/dL}$
	3. Increase > 2.0 g/dL and value > ULN
	Both criteria 2 and 3 will be flagged.
WBC count (103/microL)	1. Decrease ≥50% and value < LLN
	2. Increase ≥20% and value > ULN
Neutrophil count(10  /microL)	1. Decrease ≥20% and value < LLN
-	2. Increase ≥20% and value > ULN
Lymphocyte count (10  /microL)	1. Decrease ≥20% and value < LLN
	2. Increase ≥20% and value > ULN
Platelet count (10  /microL)	1. Decrease ≥25% and value < LLN
,	2. Increase ≥100% and value > ULN
Clinical Chemistry	 
BUN mg/dL	Increase ≥ 50% and value > ULN
Total bilirubin mg/dL	Value > 2x ULN
AST (IU/L)	Value ≥ 3x ULN
	Value > 5x ULN
	Value > 10 x ULN
	Value > 20x ULN
ALT (IU/L)	Value ≥ 3x ULN
	Value > 5x ULN
	Value > 10 x ULN
	Value > 20x ULN
AST or ALT (IU/L)	Value ≥ 3x ULN
	Value > 5x ULN
	Value > 10 x ULN
	Value > 20x ULN
AST or ALT (IU/L) + Total bilirubin (mg/dL)	AST or ALT ≥3x ULN with concurrent bilirubin > 2x ULN
Alkaline phosphatase (IU/L)	Value > 1.5x ULN
Sodium (mmol/L)	1. Decrease ≥ 10 and value <lln< td=""></lln<>
	2. Increase ≥ 10 and value >ULN
	3. Value > 155
Potassium (mmol/L)	1. Decrease ≥ 1 and value <lln< td=""></lln<>
	2. Increase $\geq 1$ and value $>$ ULN
	3. Value > 5.4 and increased 15% above baseline
	4. Value $\geq 6.0$

<sup>b Differential red blood cell count will include mean corpuscular volume (MCV), mean corpuscular hemoglobin (MCH), mean corpuscular hemoglobin concentration (MCHC), red cell distribution width (RDW).

<sup>c MBA testing will include, in addition to above tests: estimated glomerular filtration rate (eGFR) measured by MDRD at screening

All Subjects	Increase ≥ 60 msec	
QTc Change from Baseline (	ms)	
Females	Value ≥ 470 msec	
Males	Value ≥ 450 msec	
QTc (ms)		
	2. Decrease≥ 1 and value < LLN	
Magnesium (mg/dL)	1. Increase≥ 1 and value > ULN	
	2. Decrease≥ 1 and value < LLN	
Calcium (mg/dL)	
 
Increase≥ 1 and value > ULN
 

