## 5.5. Rationale for Study Population

The trial population will consist of individuals who are obese (BMI 30.0 to 40.0 kg/m^2, inclusive) These participants represent a clinically relevant population for pharmacotherapeutic weight management as they are at significant risk for weight related morbidities (such as hypertension, dyslipidemia, obstructive sleep apnea) and mortality and are likely to benefit from weight reduction. People with known cardiovascular disease (CVD) are excluded given the early stage of development and limited characterization of the safety profiles of the study regimens. A BMI > 40.0kg/m^2 is exclusionary to limit potential for occult CVD or other health issues that might increase the risk of participating in an early-stage clinical trial. People with T2DM are excluded due to the well-described confounding effect that improved glycemic control has on response to weight-loss interventions.

As first line treatment in weight management is lifestyle modification through a reduced-calorie diet and increased physical activity, only people who have tried but failed to attain weight loss goals with lifestyle modification will be eligible for participation.

Sex is an important response covariate with females typically achieving greater weight loss than males in obesity trials. Randomization will be stratified by sex to minimize potential bias. Weight loss trials have historically enrolled substantially more female than male participants. To ensure meaningful representation of both sexes, neither strata will be permitted to exceed 70% of total enrollment. Females of childbearing potential (FOCBP) are eligible for participation. Given the early stage of development and current lack of definitive embryo-fetal toxicology data for either K-757 or K-833, FOCBP must be using highly effective contraception with low user-dependence and undergo pregnancy testing at screening and specified timepoints during study participation.

Given the priority of avoiding spurious liver toxicity signals, excessive alcohol consumption, known history of liver disease (other than non-alcoholic fatty liver disease [NAFLD]), and excessive elevations in ALT, AST, and/or bilirubin at screening are exclusionary as specified in Section 8.2.

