29. Has alanine aminotransferase or aspartate aminotransferase (ALT or AST) of  $>2.0X$  upper limit of normal (ULN) or total bilirubin  $>1.5X$  ULN at the Screening visit. Note: An isolated bilirubin  $>1.5X$  ULN is acceptable if bilirubin is fractionated, and direct bilirubin is within the laboratory normal range).
30. Has serum amylase or lipase  $>1.2X$  the ULN at the Screening Visit.
31. Has a triglyceride value  $>600\text{mg/dL}$  at the Screening visit (if value is  $\geq 600\text{ mg/dL}$  and the sample was obtained in the non-fasted state, a repeat fasting determination may be obtained to assess eligibility).
32. Has a corrected QT interval to Fridericia's formula (QTcF)  $>450$  milliseconds (msec) for males and  $>470$  msec for females at screening.
33. Has a mean value for triplicate seated systolic blood pressure  $>160$  mmHg and/or diastolic blood pressure (BP)  $>95$  mmHg measured after at least 5 minutes at rest at the Screening Visit. **Note:** If a subject's BP is exclusionary on the first triplicate assessment at the Screening visit, they may have 1 repeat triplicate BP assessment at that visit after another rest of at least 10 minutes. If a participant's BP is exclusionary on 2 assessments at the Screening visit, the investigator can, at their discretion, adjust and/or add anti-hypertensive medications and re-assess triplicate BP up to twice at the Randomization visit (Visit 2). Anti-hypertensive regimens must align with the requirements detailed in Section 10.1 ( $\leq 2$  agents that do **not** include verapamil). If a participant's BP is exclusionary at the Screening visit and the randomization visit (Visit 2), they must be excluded.
34. Has known history or suspected abuse of alcohol or recreational drugs.
35. Has excessive consumption of alcohol within 6 months prior to screening ( $>14$  drinks/week for men and  $>7$  drinks/week for women, where 1 drink = 5 ounces [150 mL] of wine or 12 ounces [360 mL] of beer or 1.5 ounces [45 mL] of hard liquor) or use of soft drugs (such as marijuana or any substances containing tetrahydrocannabinol (THC) or cannabidiol (CBD)) within 3 months prior to Screening, or hard drugs (such as cocaine) within 6 months prior to Screening.

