**If participant's baseline (predose Day 1) ALT/AST value is elevated ( $>$  lab ULN)**

1. ALT or AST is  $\geq$  3X ULN **and**  $\geq$ 2X baseline **plus** any of the following:

- Total bilirubin is  $\geq 2X$  ULN\* *or*
  - INR is  $>1.5^{**}$  *or*
  - There are symptoms of potential liver injury (ie. severe fatigue, nausea, vomiting, and/or RUQ pain)
2. ALT or AST is  $\geq 8X$  ULN
  3. ALT or AST is  $\geq 5X$  ULN **and**  $\geq 3X$  baseline for  $\geq 2$  weeks

\*If a participant has Gilbert's syndrome, a direct bilirubin  $\geq 2X$  baseline will be used instead of total bilirubin.

\*\*INR criteria is not applied if a participant is on therapeutic anticoagulation.

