#### 5.11 Safety Analyses

The safety measurements include AEs, clinical laboratory assessments, vital signs, 12-lead ECG and physical examination. All summaries will be performed and reported by treatment group using the Safety Analysis Set.

No formal statistical tests or inference will be performed for safety analyses.

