#### **5.11.2** Clinical laboratory Assessments

The clinical laboratory parameters presented in Table 3 will be assessed at the specific times as outlined in the SOA (Error! Reference source not found.).

Observed values and change from baseline to each visit and time point during on-treatment period (from first dose date up to 2 weeks after the last dose of the study medication) and follow up visit in the clinical laboratory parameters for hematology and clinical chemistry will be summarized by treatment group, using descriptive statistics.

In addition, hematology and clinical chemistry parameters during on-treatment period that meet the Sponsor's pre-defined limits of change as presented in Table 4 will be summarized by treatment group, using frequency and percentage.

Clinical laboratory test parameters for hematology, clinical chemistry and urinalysis along with the associated reference ranges will be listed for individual subjects; abnormal values will be flagged as high or low in the listings. Individual measurements of laboratory tests from hematology, chemistry, and urinalysis that meet the abnormal criteria will be categorized to and listed by not clinical significant and clinical significant. Other clinical laboratory tests, such as,

virus serology, COVID-19 testing, drug screen, pregnancy, and follicle stimulating hormone (FSH) will be presented listings only.

Laboratory data will be summarized or listed in International System of Units (SI).

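### SAP Table 4 counts a stable, pre-existing total bilirubin above 2x ULN as an on-treatment limit of change, with no baseline condition and no counterpart to the Gilbert's rule in Protocol Appendix A

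*SAP*

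**What the plan says.** SAP Section 5.11.2 says that hematology and chemistry "parameters during on-treatment period that meet the Sponsor's pre-defined limits of change as presented in Table 4 will be summarized by treatment group", as frequencies and percentages. Table 4 in SAP Appendix 2 supplies the limits. Although its title refers to limits of change, the total bilirubin row is a bare value above 2x ULN, and the combined row reads "AST or ALT ≥3x ULN with concurrent bilirubin > 2x ULN". Other rows do require change; the BUN row, for example, is "Increase ≥ 50% and value > ULN".

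Three parts of the protocol bear on who meets the bilirubin limits:

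- Section 8.2, Exclusion 29 excludes total bilirubin above 1.5x ULN at screening, but an isolated elevation "is acceptable if bilirubin is fractionated, and direct bilirubin is within the laboratory normal range". No ceiling is set. The same criterion excludes ALT or AST above 2.0x ULN.
- Appendix A, in the criteria for interrupting study drug, pairs ALT or AST of at least 3x ULN with total bilirubin of at least 2x ULN. A footnote for Gilbert's syndrome says that a direct bilirubin of at least 2x "baseline will be used instead of total bilirubin".
- Section 5.5 introduces the liver-related entry criteria with "Given the priority of avoiding spurious liver toxicity signals".

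SAP Section 5.11 adds: "No formal statistical tests or inference will be performed for safety analyses".

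**The concern.** The protocol knowingly lets in participants whose total bilirubin is already high for a benign-looking reason. For the diagnosed subset it also recognises that total bilirubin is the wrong measure for judging a new liver effect. The SAP's count drops both pieces of information. An entry value above 2x ULN that never moves is reported, by arm, as having met a limit of change. If the same participant has an AST or ALT rise from any cause, the participant appears in the row that readers of a liver safety table look at first.

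Because there is no formal safety inference, the raw count is the main presentation. With 50 planned per arm, one participant is 1/50 = 2% of an arm.

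**Working it through.** The plan states no figure on this point, so there is none to reproduce. The check has two parts.

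**1. Apply the rules to hypothetical participants.** Values are multiples of ULN, except direct bilirubin (multiple of own baseline). Baseline ALT is 0.8 throughout. The last column is Appendix A's paired ALT/AST-and-bilirubin criterion.

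| Case | Total bilirubin, baseline to on-treatment | On-treatment ALT | Direct bilirubin | Gilbert's | Table 4 bilirubin row | Table 4 combined row | Appendix A pair |
|---|---|---|---|---|---|---|---|
| A | 2.2 to 2.2 | 0.8 | 1.0 | yes | counted | no | no |
| B | 2.2 to 2.2 | 3.2 | 1.0 | yes | counted | counted | no |
| C | 2.2 to 2.2 | 3.2 | 1.0 | no | counted | counted | met |
| D | 1.7 to 1.7 | 3.2 | 1.0 | yes | no | no | no |
| E | 2.2 to 3.0 | 3.2 | 2.5 | yes | counted | counted | met |

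- A is the direct effect: no change, but counted in the single row.
- B is the disagreement between the documents: counted in the combined row, while Appendix A's criterion is not met.
- C shows the limit of Appendix A. Without a Gilbert's diagnosis it also uses total bilirubin with no bilirubin baseline condition, and so agrees with Table 4 apart from at-least versus above 2x ULN.
- D shows that a stable entry value between 1.5x and 2x ULN triggers neither row.
- E shows that a real rise meets both rules.

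**2. Scale.** Inputs:

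- N = 150 (Protocol Section 7.2).
- q, the proportion with stable isolated total bilirubin above 2x ULN: assumed 1-5%.
- r, the proportion reaching AST or ALT of at least 3x ULN: assumed 1-5% and independent of q.

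Neither rate is in the documents.

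Formulas: expected in single row = N x q; expected in combined row = N x q x r; chance of at least one such combined case = 1 - (1 - q x r)^N.

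| q | r | Single row | Combined row | Chance of at least one combined |
|---|---|---|---|---|
| 0.01 | 0.01 | 150 x 0.01 = 1.5 | 150 x 0.0001 = 0.015 | 1 - 0.9999^150 = 1.5% |
| 0.03 | 0.03 | 150 x 0.03 = 4.5 | 150 x 0.0009 = 0.135 | 1 - 0.9991^150 = 12.6% |
| 0.05 | 0.05 | 150 x 0.05 = 7.5 | 150 x 0.0025 = 0.375 | 1 - 0.9975^150 = 31.3% |

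Per arm, the single row gains 1.5/3 = 0.5 to 7.5/3 = 2.5 participants on average. If q is zero, nothing is gained in either row.

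**The case against.** The best defence is that absolute multiples of ULN are a deliberately sensitive screen. Table 4 mixes value-only and change-based rows, and a liver screen should err towards counting. A baseline exclusion would also do harm: someone going from 2.2x to 6x ULN would vanish from the bilirubin row. This stands, and it is why the existing rows should stay.

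The second defence is that the context is already planned. SAP Section 5.11.2 summarises observed values and change from baseline by visit and lists individual results with reference ranges and clinical significance. Appendix A's etiology questions name Gilbert's syndrome. Randomisation means that pre-existing high bilirubin has no systematic link to arm. All this reduces the consequence. It does not make the count itself interpretable: group-level change summaries do not show which counted participants were already above the limit, and a chance imbalance of one or two participants is visible at 50 per arm.

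Four stronger readings are tempting, and the documents do not support them.

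- A reader might infer that Appendix A excludes participants with isolated high bilirubin. It substitutes a direct-bilirubin criterion, for Gilbert's syndrome only, and such a participant can still meet it.
- A reader might infer that the combined row will contain false cases. It also needs AST or ALT of at least 3x ULN, and screening values above 2.0x ULN are excluded, so high bilirubin alone cannot trigger it.
- A reader might multiply a prevalence of Gilbert's syndrome by 150. That is not the number counted, since the row needs a value above 2x ULN.
- A reader might treat the Section 5.5 remark as a rule for analysis tables. It explains eligibility; it supports the spirit of the point and no more.

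**Conclusion.** The point holds in a limited form. Table 4 ignores baseline bilirubin and omits Appendix A's Gilbert's substitution, while Exclusion 29 admits isolated high bilirubin without a ceiling. The certain consequence is in the single row: any participant with a stable total bilirubin above 2x ULN is counted with no change. The consequence for the combined row is conditional and probably rare.

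Under assumed rates of 1-5% for each component, taken as independent, the size is 1.5-7.5 participants in the single row and 0.015-0.375 expected in the combined row across the whole trial. These figures show scale only and move in proportion to the assumed rates. Efficacy analyses and formal tests are unaffected. The case for acting is that a small descriptive change makes the liver counts readable.

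**What to change.** Keep the total bilirubin row and the combined row as they stand. Add to Table 4, for each, a companion treatment-emergent count of participants who did not meet the limit at baseline or who worsened from baseline. Three details need stating before database lock:

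- In the combined row, apply the baseline condition to the bilirubin component. The entry limit on ALT and AST means the full combined limit will hardly ever be met at baseline, so a condition on the whole row would still count cases B and C.
- Define worsening, so that ordinary visit-to-visit variation around a high baseline does not qualify, while a rise such as 2.2x to 6x ULN does.
- For Gilbert's syndrome, reconcile the bilirubin criterion with Appendix A where direct bilirubin is available, say how Gilbert's status is identified, and settle the at-least versus above 2x ULN difference between the documents. Which clinical criterion is right is for the sponsor to decide.

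The cost is one extra row or footnote for each of the two counts. Direct bilirubin is in the chemistry panel (Protocol Section 15.1.5.2), scheduled at Day 1 and Weeks 4, 8, 13 and 15. It may be missing elsewhere: the content of the liver function test at Weeks 1, 2, 3, 6 and 10 is not defined in the schedule, and Appendix A's close-observation panel lists total bilirubin but not direct. The SAP should say what the companion count does in that case, for example by reporting the participant under the total-bilirubin rule with a footnote giving baseline bilirubin and Gilbert's status.
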